### 13.4 PARTICIPANT AND DATA CONFIDENTIALITY

Information about subjects will be kept confidential and managed according to the requirements of the Health Insurance Portability and Accountability Act of 1996 (HIPAA). Every reasonable effort will be made to protect the confidentiality of the subjects throughout the study.

Participant confidentiality is strictly held in trust by the participating investigators, their staff, and the sponsor(s) and their agents. Therefore, the study protocol, documentation, data, and all other information

generated will be held in strict confidence. No information concerning the study or the data will be released to any unauthorized third party without prior written approval of the sponsor.

The study monitor, other authorized representatives of the sponsor, representatives of the IRB or regulatory bodies may inspect all documents and records required to be maintained by the investigator, including but not limited to, medical records (office, clinic, or hospital) for the participants in this study. The clinical study site will permit access to such records.

The study participant's contact information will be securely stored at each clinical site for internal use during the study. In the event that a subject withdraws authorization to collect or use Personal Health Information, the investigator retains the ability to use all information collected prior to the withdrawal of authorization. At the end of the study, all records will continue to be kept in a secure location for as long a period as dictated by local IRB and Institutional regulations. The study data entry and study management systems used by clinical sites will be secured and password protected. At the end of the study, all study databases will be de-identified and archived at the sponsor.

Study participant research data from DCTclock and the Linus Platform tests will be transmitted to the sponsor or their partners as outlined below. This data will not include the participant's contact information. Rather, individual participants and their research data will be identified by a unique study identification number.

**DCTclock (tablet and pen) and Linus platform drawing tasks-** Data from these tests includes time-stamped coordinate level details of the drawing process. It is encrypted at the time of collection (either on the digital pen or iPad) and transmitted by way of a locally installed data transfer application directly to the sponsor's HIPAA compliant servers, at which point they are deleted from the input device (tablet or pen).

**Linus Platform reaction time and gait assessments-** Data from these tasks includes millisecond-level precise measurements of reaction time to tablet screen stimuli as measured by the tapping of buttons on the tablet (reaction time) and gyroscope and accelerometer readings collected on a smartphone (gait). These measurements are stored locally on the tablet/smartphone with encryption before transmission directly to the sponsor's HIPAA compliant servers, at which point they are deleted from the device.

**Linus Platform Lifestyle questionnaire and PHQ-9-** Data from these tasks include fixed 'yes/no' and 'not at all/several days/more than half the days/nearly every day' answers to questions presented to the participant on the tablet. These responses are stored locally on the tablet with encryption before transmission directly to the sponsor's HIPAA compliant servers, at which point they are deleted from the device.

**Linus Platform speech analysis-** Speech recordings and meta data about the speech session are stored locally on the tablet with encryption until they are successfully uploaded to the sponsor partner's HIPAA compliant web servers, at which point they are deleted from the device. The data is encrypted in transit and at rest on the servers. All data is hosted on AWS behind secure API gateways and is access-controlled so that only trained and approved employees can access it. Meta data only includes non-identifying information, such as time & date for the session and information about the study supplied tablet device. Audio is also sent to a HIPAA compliant transcription provider for transcription. The resulting raw audio samples, transcripts, and analysis of the voice recording transferred to the sponsor will include details such as phonation and respiratory control.

**Linus Platform eye tracking-based memory assessment-** Full face video recordings will be captured on a tablet and encrypted for storage. All videos will be stored locally at the study site. De-identified video files will be transmitted by way of a locally installed data transfer application to the secure server of a sponsor partner for analysis. No other participant details will be shared with the third party. The resulting analysis of the video recordings shared with the sponsor will include de-identified video files, gaze times and other eye movement parameters.

#### 13.4.1 RESEARCH USE OF STORED DATA

Data collected under this protocol may be used by the sponsor for future research on cognition. Access to stored data will be limited to sponsor personnel. Data will be stored using codes assigned by the investigators. Data will be kept on password-protected computers.

### 14 DATA HANDLING AND RECORD KEEPING

#### 14.1 DATA COLLECTION AND MANAGEMENT RESPONSIBILITIES

Data collection is the responsibility of the clinical trial staff at the site under the supervision of the site PI. The investigator is required to maintain detailed source documents on all subjects who are screened and/or enrolled in the study. Source documents include subject records, investigator subject trial files, as well as the results of tests and assessments. The date the subject began and exited the trial and a notation as to whether the subject completed the trial or was discontinued, including the reason for discontinuation should be included in the subject file.

All source documents should be completed in a neat, legible manner to ensure accurate interpretation of data. Dark ink is required to ensure clarity of reproduced copies. When making changes or corrections, cross out the original entry with a single line, and initial and date the change. DO NOT ERASE, OVERWRITE, OR USE CORRECTION FLUID OR TAPE ON THE ORIGINAL.

The investigator is responsible for ensuring the accuracy, completeness, legibility, and timeliness of the data reported. Case Report Forms (CRFs) are used for the collection and recording of data at the Investigative Center. The investigator is responsible for the timely completion and updating of the CRF. Data reported in the CRF derived from source documents should be consistent with the source documents or the discrepancies should be explained and captured in a progress note and maintained in the participant's official study record.

Serious Adverse Events (SAEs) are to be reported within 24 hours of knowledge of the event.

Incoming data are reviewed to identify inconsistent or missing data and adverse events. Data issues will be addressed with the site and/or during site visits. All hard copy forms and data files will be secured to ensure confidentiality. Copies of the retrieved CRFs will be kept within the Trial Master File at the sponsor or the sponsor's designee.

#### 14.2 STUDY RECORDS AND RETENTION

Study documents must be retained for a minimum of 2 years after the latter of the following two dates: The date on which the investigation is terminated or completed, or the date that the records of no longer required to support FDA approval of the device or a notice of completion of a product development protocol. No records will be destroyed without the written consent of the sponsor, if applicable. It is the responsibility of the sponsor to inform the investigator when these documents no longer need to be retained.

Investigator records shall include the following materials:

- **Correspondence:** Documentation of all verbal and written correspondence with FDA, the Sponsor, the Clinical Monitor and other investigators regarding this clinical study or any participant enrolled therein.
- **Subject records:** Signed informed consent forms, copies of all completed Case Report Forms and supporting documents (assessments, tests, etc.). Informed consent must comply with FDA regulations (21 CFR, part 50).

- **Investigational Plan (Clinical Study Protocol):** A current copy of the Clinical Study Protocol including Instructions for Use of the DCTclock device and blank case report forms.
- **Institutional Review Board (IRB) Information:** All information pertaining to IRB review and approval of this clinical study including a copy of the IRB letter approving the clinical study, a blank informed consent form approved by the IRB, and certification from the IRB Chairman that the IRB complies with FDA regulations (21CFR, Part 56)/regulatory body regulations, and that the IRB approved the clinical study protocol.
- **Investigator Agreements:** Copies of signed Investigator, Co-investigator, and Sub-Investigator Agreements, as applicable, with accompanying curriculum vitae.
- **Other:** Any other records that may be required by applicable state or federal laws.

#### 14.3 PROTOCOL DEVIATIONS

A protocol deviation is any noncompliance with the clinical trial protocol, or GCP requirements. The noncompliance may be either on the part of the participant, the investigator, or the study site staff. As a result of deviations, corrective actions are to be developed by the site and implemented promptly.

Prior approval from the sponsor is required for any deviation from the clinical study protocol except in the case of a deviation from the clinical study protocol intended to protect the life or physical well-being of a participant in an emergency. Prior approval from the reviewing IRB is also required if these changes or deviations are expected to affect the rights, safety, or welfare of human subjects.

It is the responsibility of the site to use continuous vigilance to identify and report deviations within 10 working days of identification of the protocol deviation, or within 10 working days of the scheduled protocol-required activity. All deviations must be addressed in study source documents and reported to the sponsor or designee. Protocol deviations must be sent to the local IRB per their guidelines. The site PI/study staff is responsible for knowing and adhering to their IRB requirements.

#### 14.4 PUBLICATION AND DATA SHARING POLICY

The existence of this trial is confidential, and it should not be discussed with persons outside of the trial. Additionally, the information on this document and regarding this trial contains commercially sensitive information that is confidential and may not be disclosed unless such disclosure is required by regional or national law or regulations. Subject to the foregoing, this information may be disclosed only to those persons involved in the trial who have need to know, but all such persons must be instructed not to further disseminate this information to others. These restrictions of disclosure will apply equally to all future information supplied to the investigator that is indicated as confidential.

At the conclusion of the trial, a multi-center publication may be prepared for publication in a reputable scientific journal. Per the Publications Guidelines, any presentation/ publication of any data from this study must be approved by the sponsor prior to release. No independent publications by the individual sites will be allowed. Aggregated data may be published or presented in collaboration, with authorship determined by scientific convention.

### 15 INVESTIGATOR REPORTS

The Investigator will prepare and submit the following reports:

- MDR: Medical Device Reporting of all events related to the device or device malfunctions.
- Withdrawal of IRB Approval: Withdrawal of approval shall be reported to the sponsor or designee within five working days. The Investigator will provide a written report of the reason(s) approval was withdrawn.

- Progress Reports: The Investigator may be asked to submit progress reports to the reviewing IRB that include the number of study subjects, a summary of data and complications and a general description the study progress.
- Final Report: The investigator shall submit a final report within three months of termination or completion of the study or that investigator's participation in the study, to the IRB.
- Other Reports: Upon the request of FDA, the reviewing IRB, or the sponsor or designee, the investigator will provide accurate and timely information about any aspect of the clinical study.

## 16 TERMINATION OF STUDY OR STUDY SITE PARTICIPATION

The sponsor may terminate the study at any time. If the study is terminated prior to the completion of expected enrollment for any reason, the participating centers will be notified within five working days. All participants already enrolled will continue to be followed for the planned course of study described in this protocol. The study shall be terminated following the final visit (or discharge) of the last enrolled participant.

The sponsor reserves the right to terminate study site participation and remove appropriate study materials at any time. Specific instances that may precipitate such termination include but are not limited to the following:

- Failure to meet minimum participant enrollment requirements
- Failure to comply with protocol specified procedures and documentation
- Failure to comply with Good Clinical Practice

The site Investigator may also discontinue study participation with suitable written notice to the Sponsor.

## 17 REGULATORY CONSIDERATIONS

Per 21 CFR 812.2(c)(3), diagnostic device studies are exempt as long as the sponsor complies with the requirements at 21 CFR 809.10(c) for labeling, and if the testing: (i) is noninvasive; (ii) does not require an invasive sampling procedure that presents significant risk; (iii) does not by design or intention introduce energy into a subject; and (iv) is not used as a diagnostic procedure without confirmation of the diagnosis by another, medically established diagnostic product or procedure. This study meets the criteria for exemption from the general requirements of 21 CFR 812.

**VERSION INFORMATION**

Version	Date	Significant Revisions
1	7/29/20	N/A
2	9/9/20	Addition of exploratory endpoints and a statistical description for the exploratory endpoints, clarification of safety endpoints to include that they will be analyzed and reported per test, the addition of a Linus Platform lifestyle questionnaire, a change in subject compensation, clarification of language regarding the regulatory status of DCTclock-pen, and minor editorial changes.
3	10/12/20	Addition of a new speech and voice assessment (list learning) which is administered at both visits.
4	12/12/23	Update address and contact information

1 ABBREVIATIONS

Abbreviation	Definition
AE	Adverse Event
ANOVA	Analysis of Variance
CI	Confidence Intervals
CRF	Case Report Forms
CSR	Clinical Study Report
ICC	Intraclass Correlation Coefficient
ITT	Intent-To-Treat Population
LoA	Limits of Agreement
MMSE	Mini-Mental State Exam
RBANS	Repeatable Battery for the Assessment of Neuropsychological Status
RMSD	Root Mean Squared Difference
SAE	Serious Adverse Event
SAP	Statistical Analysis Plan
TEAE	Treatment Emergent Adverse Event

2 SUMMARY

TITLE	A Randomized Crossover Study to Assess the Reliability and Equivalence of Alternate Forms of the Digital Clock Drawing Test
PREFACE	
This Statistical Analysis Plan (SAP) describes the planned analysis and reporting for Linus Health, Inc. protocol DCT216 (A Randomized Crossover Study to Assess the Reliability and Equivalence of Alternate Forms of the Digital Clock Drawing Test). This study is being completed to assess the safety and effectiveness of DCTclock in healthy adults aged 55-95.
 
The following documents were reviewed in preparation of this SAP:
 
• Clinical Research Protocol DCT216 Version 3 issued 12OCT2020• Case report forms (CRFs) issued 18NOV2020 for Protocol DCT216
PURPOSE	The purpose of this SAP is to outline the planned analyses in support of the Clinical Study Report (CSR) for protocol DCT216. Exploratory analyses not necessarily identified in this SAP may be performed to support the clinical development program. Any post-hoc, or unplanned, analyses not identified in this SAP will be clearly identified in the respective CSR.
STUDY OBJECTIVES	
The overall objectives of the study are to establish the equivalence of DCTclock-tablet to DCTclock-pen, to establish the safety of Linus Platform tests administered with a tablet or smartphone, and to collect data to enable the development and validation of Linus Platform tests.
 
Aim 1: Validate equivalence between DCTclock-pen and DCTclock-tablet for subjects with diverse levels of cognitive impairment
 
Aim 2: Characterize the safety profile of DCTclock-tablet and other Linus Platform tests
 
Aim 3: Obtain data to develop and validate Linus Platform tests

STUDY DESIGN	Randomized crossover trial consisting of two test visits separated by a washout period of 3 to 5 weeks. Subjects are randomized into two equal groups. Group 1 receives the digital pen (DCTclock-pen) version of the test at the first visit, with the tablet version (DCTclock-tablet) given at the second visit; Group 2 receives DCTclock-tablet at the first visit, followed by DCTclock-pen at the second visit. At Visit 1 (Day 0), eligibility is assessed and a version of the DCTclock test is administered based on the group allocation. A battery of Linus Platform tests and reference standard tests are also administered. At Visit 2 (Day 21-35), eligibility is assessed and the alternate version of the DCTclock test is administered based on the group allocation. A battery of Linus Platform tests is also administered, together with reference standard tests. Equivalence of DCTclock-pen and DCTclock-tablet will be tested. Linus Platform test data will also be collected to develop novel measures of cognitive and motor function and assess their accuracy in detecting impairment, construct validity, and test-retest

	
reliability. 200 subjects will be recruited to participate with the anticipation that 175 will be available for analysis.

ENDPOINTS AND ANALYSIS	
The study's primary effectiveness endpoint analysis is assessing the equivalence of DCTclock-pen and DCTclock-tablet with respect to cognitive impairment specifically by comparing the DCTclock total score (created by the DCTclock analysis algorithm) from the DCTclock-pen to the DCTclock total score from the DCTclock-tablet.
 
The study's primary safety endpoint analysis is the incidence of subjects with serious device-related adverse events from enrollment to completion of the study.
 
Secondary endpoints' analyses:
 
Agreement of DCTclock-pen and DCTclock-tablet in assessing cognitive impairment specifically by comparing each of the DCTclock composite scales (created by the DCTclock analysis algorithm) from the DCTclock-pen to the DCTclock composite scales from the DCTclock tablet. The composite scales are as follows
○ Drawing Efficiency○ Information Processing○ Simple and Complex Motor○ Spatial Reasoning 
Exploratory endpoints analyses:
 
Linus Platform individual tests will be compared to Mini-Mental State Exam (MMSE) and Repeatable Battery for the Assessment of Neuropsychological Status (RBANS) to measure agreement in assessment of cognitive status in the evaluable dataset. The list of Linus platform individual tests are as follows:
○ Linus Platform drawing tests
▪ Pre-test▪ Pathfinding test▪ Symbol test▪ Connect test▪ Tracing test○ Linus Platform decision making and reaction time tests
▪ Simple reaction time▪ Procedural reaction time▪ Go/No-go▪ PHQ-9○ Linus Platform speech elicitation tasks
▪ Complex picture description▪ Category naming▪ Object recall▪ Sentence reading

	
▪ Sustained phonation▪ Diadochokinetic rate▪ Story recall▪ List learning○ Linus Platform eye tracking-based memory assessments○ Linus Platform gait and balance assessment○ Linus Platform lifestyle questionnaire● Subjects will undergo cognitive testing with both the Linus Platform tests and the reference standard RBANS twice, where the second examination will be three to five weeks after the first examination. Linus Platform individual tests will be combined to obtain a Linus overall score (Linus score) to measure cognitive status and its agreement with MMSE and RBANS will be assessed.● Test-retest reliability of both individual Linus Platform tests and the combined Linus score will be compared to the test-retest reliability of the RBANS.
INTERIM ANALYSES	No formal interim analyses are planned for this study.
FINAL ANALYSES	All final planned analyses identified in this SAP will be completed following the final visit (or discharge) of the last enrolled subject.

3 STUDY OBJECTIVES AND ENDPOINTS

3.1 STUDY OBJECTIVES

The objectives of the study are to establish the equivalence of DCTclock-tablet to DCTclock-pen, to establish the safety of DCTclock-tablet and Linus Platform tests administered with a tablet or smartphone, and to collect the data to enable the development and validation of Linus Platform tests

3.2 STUDY ENDPOINTS

3.2.1 PRIMARY ENDPOINTS

The study's **primary effectiveness endpoint** analysis is the equivalence of DCTclock-pen and DCTclock-tablet in assessing cognitive impairment specifically by comparing the DCTclock total score (created by the DCTclock analysis algorithm) from the DCTclock-pen to the DCTclock total score from the DCTclock-tablet.

The study's **primary safety endpoint** analysis is the incidence of subjects with serious device-related adverse events from enrollment to completion of the study.

3.2.2 SECONDARY ENDPOINTS

Agreement of DCTclock-pen and DCTclock-tablet in assessing cognitive impairment specifically by comparing each of the DCTclock composite scales (created by the DCTclock analysis algorithm) for the

DCTclock-pen to the DCTclock composite scales from the DCTclock tablet. The composite scales are as follows

- Drawing Efficiency
- Information Processing
- Simple and Complex Motor
- Spatial Reasoning

3.2.3 EXPLORATORY ENDPOINTS

Linus Platform individual tests will be compared to Mini-Mental State Exam (MMSE) and Repeatable Battery for the Assessment of Neuropsychological Status (RBANS) to measure agreement in assessment of cognitive status in the evaluable dataset. The list of Linus platform individual tests are as follows:

- Linus Platform drawing tests
 - Pre-test
 - Pathfinding test
 - Symbol test
 - Connect test
 - Tracing test
- Linus Platform decision making and reaction time tests
 - Simple reaction time
 - Procedural reaction time
 - Go/No-go
 - PHQ-9
- Linus Platform speech elicitation tasks
 - Complex picture description
 - Category naming
 - Object recall
 - Sentence reading
 - Sustained phonation
 - Diadochokinetic rate
 - Story recall
 - List learning
- Linus Platform eye tracking-based memory assessments
- Linus Platform gait and balance assessment
- Linus Platform lifestyle questionnaire

Linus Platform individual tests will be combined to obtain a Linus overall score (Linus score) to measure cognitive status and its agreement with MMSE and RBANS will be assessed.

Subjects will undergo cognitive testing with both the Linus Platform tests and the reference standard RBANS twice, where the second examination will be three to five weeks after the first examination. Test-retest reliability of both individual Linus Platform tests and the combined Linus score will be compared to the test-retest reliability of the RBANS.

4 SAMPLE SIZE

The primary null and alternative hypotheses are:

$$H_0: LCI_{LLoA} \leq -\delta \text{ or } UCI_{ULoA} \geq \delta$$

$$H_1: -\delta < LCI_{LLoA} < UCI_{ULoA} < \delta$$

where $\delta = 30$ is the pre-specified maximum allowable difference, LCI_{LLoA} is the lower bound of the two-sided 95% confidence interval (CI) for the lower bound of the two-sided 95% limits of agreement (LoA), UCI_{ULoA} is the upper bound of the two-sided 95% CI for the upper bound of the two-sided 95% LoA.

The primary endpoint will be analyzed using Bland-Altman method. This study will produce LoA and associated CIs from the two measurements on each subject (further details are below). The conclusion that the two measurements are in agreement (i.e. equivalent) depends on whether the CIs constructed from the data are within the boundaries set from the maximum allowable difference. An evaluable sample size of 41 subjects achieves at least 90% power to detect agreement when the confidence level of the LoA is 95%, the confidence level of the CIs about the LoA is 95%, and the maximum allowable difference is 30 ($\delta = 30$). The mean and standard deviation of the sample differences are anticipated to be 10 and 7, respectively.

Accordingly, approximately 175 subjects will be enrolled in order to obtain a DCTclock-tablet training dataset of at least 100 subjects and a DCTclock-tablet validation dataset of greater than 41 evaluable subjects.

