6.2 EVALUABLE POPULATION

The evaluable population for this study includes all ITT subjects who undergo cognitive testing with both DCTclock-pen and DCT-clock table and the Linus Platform tests. Given that no initial tablet model needs to be trained, the evaluable population is the primary analysis population for effectiveness.

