6.3 VALIDATION POPULATION

The validation population is a randomly selected subset of 50 subjects from the evaluable population. If there is a need to train a tablet specific model, this will become the primary population for evaluating effectiveness.

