9 EFFECTIVENESS ANALYSES

9.1 PRIMARY EFFECTIVENESS VARIABLE AND ANALYSES (CONSTANT VARIANCE)

Agreement of DCTclock-pen and DCTclock-tablet in assessing cognitive impairment will be assessed by using the Bland-Altman method on the DCTclock total score. The following hypothesis test will be carried out:

$$H_0: Lower_{LoA} \leq -\delta \text{ or } Upper_{LoA} \geq \delta$$

$$H_1: -\delta < Lower_{LoA} < Upper_{LoA} < \delta$$

where $\delta = 30$ is the pre-specified maximum allowable difference, $Lower_{LoA}$ is the lower bound of the two-sided 95% LoA, $Upper_{LoA}$ is the upper bound of the two-sided 95% LoA. The conclusion that the two measurements are in agreement (i.e. equivalent) depends on whether the two-sided 95% CIs of each (lower, upper) LoA are within the boundaries set from the maximum allowable difference.

Specifically, Bland-Altman analysis will consist of the following:

1. Calculate the paired difference in scores between the two tests (i.e., Discrepancy scores) for each subject.
2. Calculate the mean of these paired differences.
3. Calculate the average of the two test results for each subject.
4. Plot the paired differences (y-axis) vs. the average of the two test results (x-axis). This is commonly called the Bland-Altman plot.
5. Calculate a two-sided 95% LoA of the paired differences as: mean difference +/- 1.96*standard deviation (sd) of the differences.

6. Calculate two-sided 95% CI of each (lower, upper) LoA. The formulas for calculating these CIs are as follows:

*Lower: mean difference – 1.96 * sd – (t0.975, N – 1) * sd * sqrt(1/N + 1.96²/(2 * (N – 1))).*

*Upper: mean difference + 1.96 * sd + (t0.975, N – 1) * sd * sqrt(1/N + 1.96²/(2 * (N – 1))).*

where $t0.975, N – 1 * sd$ is the upper 0.025 critical value of the t distribution with $N-1$ degrees of freedom and where N is the sample size.

7. The conclusion that the two measurements are in agreement (i.e. equivalent) depends on whether the CIs constructed from the data are within the boundaries set from the maximum allowable difference. Success is declared on the primary endpoint if the lower CI of the lower LoA is >-30 , and the upper CI of the upper LoA is $<+30$.

The Evaluable Population will be used for these analyses.

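### The stated 90% power at 41 subjects comes out of a planning approximation; the SAP's own success rule gives about 87.5% at 41 and reaches 90% at 45 (minor)

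*SAP*

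**What the plan says.** SAP section 4 bases the sample size on a Bland-Altman agreement test with a maximum allowable difference of 30, 95% limits of agreement and 95% confidence intervals about those limits. It states: "An evaluable sample size of 41 subjects achieves at least 90% power to detect agreement". The planning inputs follow: "The mean and standard deviation of the sample differences are anticipated to be 10 and 7, respectively". The section then uses 41 as a floor, asking for "a DCTclock-tablet validation dataset of greater than 41 evaluable subjects". Protocol 10.3.3 makes the same statements. Neither document names a power formula or software.

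The decision rule is in SAP 9.1. Step 6 reads "Calculate two-sided 95% CI of each (lower, upper) LoA" and gives the formula, with a t quantile on N − 1 degrees of freedom. Step 7 adds: "Success is declared on the primary endpoint if the lower CI of the lower LoA is" above −30 and the upper confidence bound of the upper limit is below +30. Section 4 writes its hypotheses in terms of the same two bounds, so there is no doubt about which rule the power should describe.

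On the sizes to be analysed, SAP section 2 says "200 subjects will be recruited to participate with the anticipation that 175 will be available for analysis", and SAP 6.2 says "the evaluable population is the primary analysis population for effectiveness". SAP 6.3 defines a random validation subset of 50 as a fallback: "If there is a need to train a tablet specific model, this will become the primary population for evaluating effectiveness". Protocol 10.2 makes that 50-subject set primary.

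**The concern.** A power statement should describe the test that will be run. At the plan's own mean, SD and margin, the rule in SAP 9.1 does not have 90% power with 41 subjects. Because 41 also serves as the lower bound for the validation set, the shortfall carries into that floor: a set of 42, 43 or 44 would satisfy section 4 and still miss the stated target. Section 4 also gives no power for 50 or for about 175, so a reader cannot see from the plan whether the shortfall touches any analysis that will be done.

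**Working it through.** **Inputs.** Margin δ = 30, mean difference 10, SD 7 (SAP 4). Limits of agreement are mean ± 1.96 × sd, and each has a two-sided 95% interval with standard error sd × sqrt(1/N + 1.96²/(2(N − 1))) (SAP 9.1 steps 5 and 6). The calculation assumes that the paired differences are normal with constant variance.

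**Step 1: reproduce the plan's figure.** The common planning approximation compares the distance from the true limit to the margin with the standard error, using a noncentral t distribution. At N = 41:

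- SE = 7 × sqrt(1/41 + 3.8416/80) = 7 × sqrt(0.02439 + 0.04802) = 7 × 0.2691 = 1.884.
- Upper limit: (30 − 10 − 1.96 × 7)/1.884 = 6.28/1.884 = 3.334.
- Lower limit: (30 + 10 − 1.96 × 7)/1.884 = 26.28/1.884 = 13.95. This limit is so far from its margin that it costs no power.
- Power ≈ P(T > 2.021), with T noncentral t on 40 df and noncentrality 3.334, which is 90.2%.

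At N = 40 the same calculation gives 89.4%. So 41 is exactly the smallest N at which this approximation reaches 90%. That this method was used is an inference, since no method is named.

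**Step 2: power of the rule in SAP 9.1.** Write K(N) = 1.96 + t(0.975, N − 1) × sqrt(1/N + 1.96²/(2(N − 1))). Success requires mean + K × s < 30 and mean − K × s > −30, where s is the sample SD. At N = 41, K = 1.96 + 2.021 × 0.2691 = 2.504, so with a mean of 10 the rule passes only if s is below 20/2.504 = 7.99. Integrating the normal distribution of the sample mean over the chi-square distribution of s² gives:

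| N | Power, SAP 9.1 rule |
|---|---|
| 40 | 86.7% |
| 41 | 87.5% |
| 42 | 88.2% |
| 43 | 88.9% |
| 44 | 89.6% |
| 45 | 90.2% |
| 50 | 92.9% |
| 175 | over 99.9% |

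Simulation with 2,000,000 draws agrees: 0.8747 at 41, 0.9021 at 45 and 0.9287 at 50.

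**Step 3: why the two differ.** A large sample SD moves the estimated upper limit towards the margin and also widens its interval. The approximation treats these as separate sources of error, whereas in the rule they move together. At N = 41 the difference is 90.2 − 87.5 = 2.7 points.

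**Step 4: sensitivity to the inputs.** The inputs are whole numbers. Moving both within their rounding range, from mean 9.5 with SD 6.5 to mean 10.5 with SD 7.5, power runs as follows:

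- N = 41: 97.9% down to 64.1%.
- N = 50: 99.3% down to 72.0%.
- N = 175: at least 99.6% throughout.

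At N = 41 the rule does reach 90% with SD 6.89 (mean 10) or with mean 9.69 (SD 7). With the mean held at 10, power falls below 90% once the SD exceeds about 7.14 at N = 50, or about 8.36 at N = 175.

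**The case against.** The strongest reply is that nothing was miscalculated. From the SAP's own inputs a standard planning formula returns 41, and sample-size formulas are routinely approximate. That stands. A reader might infer an arithmetic slip or a wrong input, and the documents do not support that. What remains is that the approximation overstates the power of the stated rule, and that the plan does not say its figure is approximate.

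A second reply is that the gap is smaller than the uncertainty in the inputs: SD 6.89 or mean 9.69 would round to the stated values and give 90%. This also stands, and it is why the point is minor.

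A third is that the floor never binds, because both documents fix the validation set at 50. That is right in practice. The floor is still stated in section 4 and still admits sizes that miss the target it is meant to secure.

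A fourth is that the protocol gives no formula for the confidence interval of the limits, so 87.5% tests its power sentence against a formula found only in the SAP. That is fair. The main correction belongs in the SAP, and the protocol edit is there to keep the two documents aligned.

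**Conclusion.** The point holds as a minor correction to a stated figure. Under normal, constant-variance differences with mean 10 and SD 7, the SAP 9.1 rule has 87.5% power at 41 and needs 45 for 90%; sizes 42 to 44, which the floor allows, give 88.2% to 89.6%.

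A reader might infer that the trial is underpowered. The documents do not support that: at the planning inputs the 50-subject set has 92.9% power and the evaluable set of about 175 has over 99.9%. The 50-subject set has little reserve if the SD is above 7, but that reflects uncertainty in the inputs and not the choice of power formula. A reader might also infer that the interval formula in step 6 has to change. It does not: the formula is fully specified and consistent with the hypotheses in section 4, and only the power attached to it is overstated.

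**What to change.** In SAP section 4, with a matching edit in protocol 10.3.3:

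- Restate 41 as giving about 87% power under the SAP 9.1 rule; or give 45 as the size for 90% and set the validation-set floor at 45 or more.
- Quote power at the sizes that would be analysed: 92.9% at 50 and over 99.9% at about 175, both at mean 10 and SD 7.

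The cost is a few restated figures. The step 6 formula, the success rule and enrolment do not change.
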